8. STATISTICAL METHODS AND DETERMINATION OF SAMPLE SIZE

8.1 General Considerations for Data Analysis

All statistical processing will be performed using the SAS® system (Version 9.12 or higher). Up to 15 subjects will be enrolled in this study to ensure a minimum of 10 subjects complete the study. The primary efficacy analysis of the study will be the determination of the NPRS from baseline to Visit 7 (Day 36).

Secondary efficacy endpoints will be evaluated using descriptive statistics. No interim or subgroup analyses are planned.

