- Request the subject to complete Day 1 of the diary and review for completeness and accuracy

Visit 3 to 8

Clinic visit with a radiation oncologist once a week till the end of treatment.

All study visits will have a \pm 2 day visit window during the radiotherapy.

- Query for adverse events
- Update concomitant medications and PEG tube usage
- Review the diary for the previous week
- Query for treatment regimen compliance
- Collect the study medication and weigh the study medication to determine usage
- Administer the QoL Questionnaire
- Administer the Numerical Rating Pain Scale (NRPS) as related to mouth pain and pain with swallowing. The NRPS will be recorded daily by the subjects between study visits
- Inspect the oral cavity and grade mucositis according to the RTOG Scale
- Record the subject's tolerability to the study drug
- Instruct the subject to return for the next study visit with study medication container and diary

Follow-up Period

Visit 9 to 10

Clinic visit with a radiation oncologist every other week after completion of radiotherapy until either mucositis resolves or it reaches Visit 10, whichever is earlier.

All study visits will have a \pm 2 day window during the follow-up period.

- Query for adverse events
- Update concomitant medications and PEG tube usage
- Review the diary for the previous week.
- Query for treatment regimen compliance
- Collect the study medication and weigh the study medication to determine usage
- Administer the QoL Questionnaire
- Administer the Numerical Rating Pain Scale (NRPS) as related to mouth pain and pain with swallowing. The NRPS will be recorded daily by the subjects between study visits.
- Inspect the oral cavity and grade mucositis according to the RTOG Scale
- Record the subject's tolerability to the study drug
- Instruct the subject to return for the next study visit with study medication container and diary

Trial Contacts

Name	Affiliation / Address	Responsibility
Santalis Corporation	[name] ☎ [contact] ✉ [contact]	Sponsor
[name].	Santalis Corporation [name] ☎ [contact] ✉ [contact] e-mail: [contact]	Sponsor Manager and contact for SAEs

Table of Contents

Contents

TITLE PAGE	1
Trial Contacts	6
Table of Contents.....	7
List of Tables.....	9
List of Figures	10
LIST OF ABBREVIATIONS AND DEFINITION OF TERMS	11
1 INTRODUCTION.....	12
1.1 Oral Mucositis	12
1.2 Santalis Oral Mucositis Treatment.....	12

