3. STUDY PLAN

3.1 Overall Study Design

This trial will be a single-center, open-label, proof of concept trial to evaluate the efficacy, safety and tolerability of SAN005 treatment regimen when administered to adults at least 18 years of age for the prevention and treatment of oral mucositis.

Subjects will enter the Screening Period once the informed consent process has been completed. Subjects who are scheduled to receive radiation with or without concurrent chemotherapy and meet all of the inclusion criteria and none of the exclusion criteria will be eligible for the study:

Once subject eligibility is confirmed the subject will start SAN005 treatment on Day 1 of their radiation treatment. All subjects will receive active medication in the study with the first dose administered on Day 1.

Subjects will be instructed on the administration of study medication thrice daily till oral mucositis resolves. Subjects will return to the clinic once a week while receiving radiation and then once every two weeks once their radiation has been completed and then until their mucositis has resolved for the Final Study Visit.

Preliminary Efficacy Evaluation will be the severity of pain rated by the NRPS and mucositis grade by RTOG criteria at Visit 7 (Day 36). Additional secondary efficacy evaluations will include the severity of pain rated by the NRPS and mucositis grade by RTOG criteria at each study visit, frequency of the PEG tube for feeding during the duration of treatment and weight loss from baseline through Visit 5 and 7. The time of mucositis onset and duration will also be used in assessing efficacy. Additional secondary and exploratory endpoints will be outlined in the statistical analysis plan. The overall efficacy is determined by comparing the data to historical controls.

Safety will be assessed by evaluating adverse events (AEs) with respect to severity, duration, and relationship to study drug. In addition tolerability evaluations will be performed at each study visit.

During the active treatment period, subjects will return to the study site according to the study schedule for interim assessments, review of subject dosing diaries, and assessment of concomitant medication and adverse events (AEs).

The study design is summarized in Figure 3-1.

Figure 3-1 **Study Design**

Pretreatment	Treatment		Follow-up
Day 0	Day 1 Baseline	Day 8,15,22,29,36,43 (\pm 2 day, weekly)	Every other week until mucositis resolves or it reaches Visit 10

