6.0 VISIT SCHEDULE AND ASSESSMENTS

6.1 Study Procedures

The visit schedule and assessments are summarized in Table 5-1. A patient will have a maximum of 10 visits: a pretreatment Visit (Visit 1), weekly treatment visits (Visit 2 – 8), and if the mucositis persists, follow-up visits (Visit 9 -10) every other week until the patient's mucositis has resolved which is estimated out to be approximately 9 to 11 weeks after Day 1 treatment initiation.

Source documents will be completed at each patient's visit, and the data captured in the source documents will be subsequently entered into the case report forms (CRFs) by the Investigator or designee.

Table 6–1 Time and Events

Footnotes to Table 1: Time and Events

- ^a Site staff will follow the requirements of the local IRB if required to obtain informed consent from the subjects.
- ^b Only pertinent medical history will be recorded for each subject including smoking history and alcohol intake.
- ^c A serum pregnancy test will be completed for all women of child-bearing potential before radiotherapy simulation.
- ^d Adverse events will be collected after the subject's first treatment and throughout the trial.

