6.2 Study Visits and Contacts

6.2.1 Treatment Period: Visit 2 Baseline (Day 1 or at Validation)

The following procedures will be completed at Visit 2 (Baseline) after the informed consent process has been completed and the informed consent form signed.

- Review and update the subject's medications and PEG tube usage
- Inspect the oral cavity for any abnormalities that could potentially confound study results
- Administer the Numerical Rating Pain Scale (NRPS) as related to mouth pain and pain with swallowing. The NRPS will be recorded daily by the subjects between study visits.
- Administer the QoL Questionnaire
- Provide the subject with the products, directions for use and diaries. Be sure to weigh the study medication container(s) to ensure an accurate weight of the unused medication is obtained at Visit 1 and for future comparisons
- Review Day 1 of the diary for completeness and accuracy

6.2.2 Treatment Period: Visit 2 to 8

During the treatment period, subjects will be evaluated by the treating physician once a week. If it is not possible for the subject to come in for the scheduled study visit, the visit can be conducted 2 days earlier or later, but the study personnel should attempt to get the subject back on schedule at the next study visit.

The following procedures will be completed.

- Query for adverse events
- Update concomitant medications and PEG tube usage
- Review the diary of the previous week
- Query for treatment regimen compliance
- Collect the study medication and weigh the study medication to determine usage
- Dispense study medication, as necessary
- Administer the QoL Questionnaire
- Administer the Numerical Rating Pain Scale (NRPS) as related to mouth pain and pain with swallowing. The NRPS will be recorded daily by the subjects between study visits.
- Inspect the oral cavity and grade mucositis according to the RTOG Scale
- Record the subject's tolerability to the study drug
- Instruct the subject to return for the next study visit with study medication container and diary

6.2.3 Follow-up Period: Visit 9 to 10

Clinic visits with a radiation oncologist every other week after completion of radiotherapy until mucositis has resolved.

Study visits will have a \pm 2 day window during the follow-up period.

- Query for adverse events
- Update concomitant medications and PEG tube usage
- Review the diaries of the previous week.
- Query for treatment regimen compliance

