8.5.4 Efficacy Analysis

The primary data analysis set for efficacy analyses will be the PP defined in Section 8.4.3. The primary analysis will be the determination of the severity and intensity of mucositis from Baseline to Visit 7 (Day 36).

The secondary efficacy endpoints analysis will be summarized using standard statistical methods and outlined in the Statistical Analysis Plan (SAP). In general, categorical endpoints will be tabulated by number, percentage, and a 95% 2-sided confidence interval (exact methodology) will be estimated. Continuous endpoints (i.e., percent change from baseline) may be summarized using descriptive statistics (N, mean, median, standard deviation, and range).

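### Mucositis duration can be right-censored at Visit 10, but the plan gives no censoring rule and names only summaries that do not allow for it

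*Combined protocol and SAP*

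**What the plan says.** Section 3.1 makes duration an efficacy measure: "The time of mucositis onset and duration will also be used in assessing efficacy". It adds that overall efficacy is judged against historical controls.

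Three places cap observation:
- Synopsis, Follow-up Period: visits run "until either mucositis resolves or it reaches Visit 10, whichever is earlier".
- Figure 3-1: "Every other week until mucositis resolves or it reaches Visit 10".
- Section 6.1: "A patient will have a maximum of 10 visits", with resolution expected "approximately 9 to 11 weeks after Day 1 treatment initiation".

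Other places state no cap. Section 6.2.3 has "Clinic visits with a radiation oncologist every other week after completion of radiotherapy until mucositis has resolved", although its heading covers only Visits 9 and 10. The design paragraph of the synopsis and the text of Section 3.1 likewise carry visits on until resolution.

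On method, Section 8.1 says "Secondary efficacy endpoints will be evaluated using descriptive statistics". Section 8.5.4 says continuous endpoints, with percent change from baseline as the instance, "may be summarized using descriptive statistics (N, mean, median, standard deviation, and range"), and leaves the detail of secondary endpoints to a SAP. The text available defines neither onset nor resolution by RTOG grade, gives no censoring rule and names no time-to-event method.

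**The concern.** A subject whose mucositis persists at Visit 10, or who withdraws before it resolves, has a duration known only to exceed a certain value. A plain mean has no place for such a value. The analyst must either leave the subject out or treat the last visit as the date of resolution. Both shorten the longest episodes, and a shorter duration looks better for the product.

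The situation is likely to arise even in a small study. If 10%, 20% or 30% of subjects are unresolved at Visit 10, the chance of at least one among 10 completers is 65%, 89% or 97%. The trial is open-label and one or two subjects can move a mean of 10, so the rule should be fixed before the data are seen.

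**Working it through.** **1. The plan's cut-off.** Visits 9 and 10 fall 14 and 28 days after radiotherapy ends. Assume a seven-week course ending on Day 49.
- Visit 9 is Day 63: (63 − 1)/7 = 8.9 weeks after Day 1.
- Visit 10 is Day 77: (77 − 1)/7 = 10.9 weeks after Day 1.

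This reproduces the 9 to 11 weeks of Section 6.1. Counting from Visit 8 (Day 43) instead gives Days 57 and 71, or 8.0 and 10.0 weeks. A cut-off 28 days after radiation is therefore a fair reading.

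**2. Truncation bias in the mean.** The documents give no resolution rate, so this step rests on assumptions. Let T, the time from end of radiation to resolution, be log-normal with median m and log-SD s = 0.5. The cut-off is c = 28 days, and z = ln(28/m)/0.5.
- True mean: M = m·exp(s²/2) = 1.133m
- Unresolved at Visit 10: 1 − Φ(z)
- Mean with unresolved set to Visit 10: M·Φ(z − s) + 28·[1 − Φ(z)]
- Mean with unresolved dropped: M·Φ(z − s)/Φ(z)

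For m = 21: z = 0.575, Φ(z) = 0.7175, Φ(z − s) = 0.530 and M = 23.80.
- Set to Visit 10: 23.80 × 0.530 + 28 × 0.2825 = 20.52, a bias of −3.3 days.
- Dropped: 23.80 × 0.530/0.7175 = 17.58, a bias of −6.2 days.

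| Median m (days) | Unresolved at Visit 10 | True mean | Bias, set to Visit 10 | Bias, dropped |
|---|---|---|---|---|
| 14 | 8% | 15.9 | −0.7 | −1.8 |
| 21 | 28% | 23.8 | −3.3 | −6.2 |
| 28 | 50% | 31.7 | −7.9 | −12.1 |

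A second model gives the same pattern. It takes onset uniform on Days 8 to 22 and gamma resolution times (shape 3) after Day 49. With 10%, 20%, 30% and 50% unresolved, the bias in mean duration is −0.7, −1.9, −3.5 and −8.6 days when set to Visit 10, and −2.2, −4.4, −7.0 and −13.8 days when dropped.

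**3. The median.** In the gamma model the median is unbiased at 10%, 20% and 30% unresolved if those subjects are kept at Visit 10. It is low by 1.7 days at 40% and by 4.2 days at 50%. If unresolved subjects are dropped it is low throughout: by 1.1, 2.7, 4.7 and 10.3 days at 10%, 20%, 30% and 50%.

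**4. Late detection.** Resolution between visits is recorded only at the next one. In the log-normal model, record every resolution at 14 or 28 days and set unresolved subjects to 28. The recorded mean is 14·P(T ≤ 14) + 28·P(T > 14).
- m = 14: 14 × 0.500 + 28 × 0.500 = 21.0, against 15.9 (net +5.1)
- m = 21: 14 × 0.209 + 28 × 0.791 = 25.1, against 23.8 (net +1.3)
- m = 28: 14 × 0.083 + 28 × 0.917 = 26.8, against 31.7 (net −4.9)

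The gamma model, which also records onset at weekly visits, gives net +1.8, −0.2, −2.5 and −9.0 days at 10%, 20%, 30% and 50% unresolved. The sign of the net error therefore depends on how many subjects are unresolved.

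**The case against.** The strongest reply is that the plan states no wrong method. Section 8.5.4 is permissive, cites change scores rather than times, and defers to a SAP. A Kaplan-Meier curve without a test is itself descriptive, so Section 8.1 does not exclude it. This stands: the defect is a missing rule, not a mandated error. It does not dispose of the point, because the only summaries named cannot accommodate a censored value, and the text available supplies no rule to go with them.

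A reader might go further and infer that the plan builds in a bias in favour of SAN005. The documents do not support that, for four reasons:
- The median is safe when unresolved subjects are kept and are clearly fewer than half.
- Two-weekly detection lengthens recorded durations and can outweigh truncation.
- The source, follow-up and summary method of the historical controls are not stated. Controls cut off in the same way would carry a similar bias.
- The cap itself is contradicted by the passages that continue visits until resolution.

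Scale also matters. With 10 subjects the standard error of the mean, M·√(exp(s²) − 1)/√10, is about 2.7 days at m = 14 and 4.0 days at m = 21. The set-to-Visit-10 bias (0.7 and 3.3 days) is below that; the bias from dropping subjects at m = 21 (6.2 days) is not. Section 8.2 says the study is not powered, and duration is one secondary measure among several. These facts limit the importance of the point but do not remove it.

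**Conclusion.** The concern holds in limited form. Duration is an efficacy measure whose observation ends at about Day 71 to 77 under the capped wording. The plan neither defines it nor says how unresolved or withdrawn subjects enter.

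Truncation alone lowers a plain mean by about 0.7 to 8 days when unresolved subjects are set to Visit 10, and by about 2 to 12 days when they are dropped. These figures assume log-normal resolution with medians of 14 to 28 days after radiation, log-SD 0.5 and a 28-day cut-off. The upper end of each range, with half unresolved, lies at the edge of the plan's own 9 to 11 week expectation. Neither the net error after late detection nor the direction of the comparison with historical controls can be settled from the documents.

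This should be corrected, but it affects a secondary measure only; the primary assessment at Visit 7 is untouched.

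**What to change.** Add one paragraph to Section 8.5.4, or to the SAP, that:
- defines onset and resolution by RTOG grade;
- summarises time to onset and duration by Kaplan-Meier, or by interval-censored estimates since visits are 7 to 14 days apart, giving the median with 95% CI and stating where it is not reached;
- censors unresolved or withdrawn subjects at their last graded visit, noting that withdrawal for adverse events or noncompliance (Section 6.4) may be informative;
- reports the number unresolved at Visit 10, and does not use a mean that ignores censoring as the efficacy summary;
- applies the same cut-off and rule to the historical controls where their data allow.

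Separately, reconcile the passages that cap follow-up at Visit 10 (synopsis Follow-up Period, Figure 3-1, Section 6.1) with those that continue until resolution (synopsis design paragraph, Section 3.1 text, Section 6.2.3).

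The cost is a paragraph of wording and no new trial data. The drawback is small: with 10 to 15 subjects the interval will be wide and the median may not be reached.

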8.2 Sample Size and Power Considerations

This study is not designed or powered for statistical considerations.

8.3 Treatment Assignment and Blinding

This is an open-label study therefore, no blinding is required.

8.4 Analysis Populations

8.4.1 Intent-to-Treat Analysis Set

The Intent-to-treat (ITT) Analysis Set is defined as all subjects enrolled and that receive at least one treatment of the investigative study regimen.

8.4.2 Full Analysis Set

The Full Analysis Set (FAS) is defined as all subjects who receive at least one administration of the investigative study regimen and who had at least one post-Baseline efficacy assessment. The FAS population will be the primary population used for efficacy analysis.

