3.2 Study Endpoints

Primary efficacy will be assessed by the numerical rating pain scale (NRPS) and RTOG mucositis grade at Visit 7 (Day 36).

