6.4 Withdrawals

The following medical and other reasons justify a premature termination (by subject or investigator) of any of the study products:

- Adverse event (including any SAE, clinically significant AE, intercurrent illness, or other medical condition that indicates to the investigator that continued participation is not in the best interest of the subject);
- Death;
- Lost to follow-up;
- Noncompliance with study medication dosing regimen, protocol requirements, or study-related procedures;
- Investigator discretion in case of occurrence of any medication condition, requirement for prohibited concomitant medication or treatment, or circumstances that would not allow the subject to adhere to protocol requirements;
- Pregnancy;
- Study terminated by Sponsor;
- Withdrawal of consent;

If a subject withdraws from the study, all efforts will be made to complete a final evaluation, if possible. Subjects discontinued due to an AE will be followed until the AE is resolved, a reasonable explanation is provided for the event, or the subject is referred to his/her own primary medical doctor. The specific AE in question will be recorded on the appropriate CRF. All subjects who are withdrawn should complete return to the clinic for a final assessment.

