7.6.1 Pain Assessment

At each Study Visit the NRPS will be recorded for mouth pain and pain upon swallowing. For the primary efficacy assessment the NRPS scale at baseline will be compared to Week 5. Subjects that complete at least 80% of treatments as determined by the diary and confirmed by the weight of the returned study product will be included in the efficacy analysis.

If possible, the same investigator who completes the scoring at Baseline should complete all subsequent assessments for the patient.

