8.4.3 Per Protocol Analysis Set

The Per Protocol Analysis Set (PP) is defined as all subjects in the FAS who do not have any major protocol violations, including:

- Violations of inclusion/exclusion criteria;

- Use of prohibited concomitant medications;
- Noncompliance (ie, <80% compliant with study treatment);
- Failure to provide a clinical observation at Week 5 (\pm 2 day, Visit 7);

The PP will be a secondary population used for efficacy analysis.

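### No rule covers a missing Visit 7 value, so the primary result rests only on subjects observed at Visit 7, whichever analysis set is primary

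*Combined protocol and SAP*

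**What the plan says.** **Endpoint.** Section 3.2: "Primary efficacy will be assessed by the numerical rating pain scale (NRPS) and RTOG mucositis grade at Visit 7 (Day 36". For pain, 7.6.1 adds: "For the primary efficacy assessment the NRPS scale at baseline will be compared to Week 5". Section 8.1 is looser: "The primary efficacy analysis of the study will be the determination of the NPRS from baseline to Visit 7 (Day 36". Figure 3-1 in section 3.1 places Visits 3 to 8 at "Day 8,15,22,29,36,43", so Visit 7 is the fifth post-baseline visit.

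**Analysis sets.** Section 8.4.2 describes the FAS as dosed subjects "who had at least one post-Baseline efficacy assessment. The FAS population will be the primary population used for efficacy analysis". Section 8.4.3 calls the Per Protocol (PP) set secondary and lists among its exclusions "Failure to provide a clinical observation at Week 5". Section 8.5.4 says the opposite about which set leads: "The primary data analysis set for efficacy analyses will be the PP defined in Section 8.4.3". Section 8.4.1 defines an ITT set of everyone enrolled and treated, but no analysis is assigned to it.

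**Other filters.** Section 7.6.1 restricts the efficacy analysis to subjects who took 80% or more of their treatments. Section 4.1 excludes dropouts for poor compliance and patients whose radiotherapy was interrupted for over two weeks.

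**Leavers.** Section 6.4: "If a subject withdraws from the study, all efforts will be made to complete a final evaluation, if possible". Nothing says that this evaluation stands in for Visit 7.

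**The concern.** A subject who leaves after Visit 3, 4, 5 or 6 belongs to the FAS but has no primary value. The plan gives no imputation, no longitudinal model and no failure rule for that subject. An analyst following the text would compute the Visit 7 summary from whoever was seen at Visit 7 and label it FAS.

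This matters because of why subjects leave. Section 6.4 lists adverse events and noncompliance. Section 7.3.1 discontinues subjects whose reaction to the product recurs. Section 1.1 itself says that mucositis impairs treatment compliance and leads to radiotherapy breaks. Subjects with bad mucositis, or who cannot tolerate the rinse, are therefore plausible candidates to be missing at Day 36. The trial has one arm, and section 3.1 judges efficacy against historical controls, so no concurrent group shares the same attrition. A Visit 7 figure on observed subjects may look too favourable in that comparison.

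**Working it through.** **Step 1: can an FAS subject lack the primary value?** FAS entry needs one dose and one later efficacy assessment. The first scheduled one is Visit 3, Day 8; the endpoint is at Day 36. Yes, for anyone who leaves between those visits.

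**Step 2: is there a rule for that subject?** Setting 3.2, 6.4, 7.6.1, 8.1, 8.4.1 to 8.4.4 and 8.5.4 side by side, none gives one. Sections 3.1 and 8.5.4 refer to a SAP for secondary and exploratory endpoints, not for the primary analysis, and no separate SAP text is in the documents.

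**Step 3: does the choice of set remove the problem?** If the FAS is primary (8.4.2), subjects without Visit 7 drop out by default. If PP is primary (8.5.4), they drop out by stated exclusion (8.4.3). In both cases no analysis counts every treated subject at the primary time point.

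**Step 4: how many could be missing?** The plan's own figures are 15 enrolled so that 10 complete (4.1, 6.6, 8.1). The implied allowance is 1 − 10/15 = 5/15 = 33.3%. Back-checking, 10 / (1 − 1/3) = 15. This is only a consistency check, because no dropout rate is stated.

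**Step 5: effect on a proportion.** Let N be all treated subjects, m those without a Visit 7 grade, and x the successes among the N − m observed.

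- Observed: x / (N − m)
- Worst case: x / N
- Best case: (x + m) / N
- Distance between bounds: m / N, whatever x is

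With N = 15, and assuming m = 5 (every allowed non-completer lost before Visit 7) and x as shown, with exact (Clopper-Pearson) 95% intervals:

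| Assumed x | Observed | Worst case | Best case |
|---|---|---|---|
| 2 | 2/10 = 20% (2.5–55.6%) | 2/15 = 13.3% (1.7–40.5%) | 7/15 = 46.7% (21.3–73.4%) |
| 4 | 4/10 = 40% (12.2–73.8%) | 4/15 = 26.7% (7.8–55.1%) | 9/15 = 60% (32.3–83.7%) |
| 6 | 6/10 = 60% (26.2–87.8%) | 6/15 = 40% (16.3–67.7%) | 11/15 = 73.3% (44.9–92.2%) |

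The bounds are 5/15 = 33 points apart in each row. With 1, 2 or 3 missing of 15 they are 7, 13 or 20 points apart.

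**Step 6: effect on the NRPS mean.** If leavers would have scored d points worse than those observed, the all-treated mean is (m/N) × d worse. With d = 3 (an assumption), m = 5 gives 5/15 × 3 = 1.0 point; m = 1, 2 or 3 gives 0.2, 0.4 or 0.6.

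**The case against.** The strongest reply is that this is a 15-subject, open-label proof of concept which 8.2 says is not powered. Its Visit 7 summary is descriptive, and if 8.5.4 governs, the exclusion is openly stated. Evaluations at withdrawal are planned, so data on leavers should often exist. All of that is true, but an unpowered trial rests entirely on its descriptive figures, and their denominator decides what those figures mean. Stating an exclusion does not make the remaining subjects representative.

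A reader might infer several stronger things that the documents do not support:

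- *Early leavers count nowhere.* They count in the Safety Analysis Set (8.4.4), in visit attendance and compliance (8.5.2), in adverse event summaries (8.5.5) and in the by-visit NRPS and RTOG summaries (3.1).
- *The result is a completer analysis.* Follow-up can run to Visit 10. A subject who leaves after Day 36 has a primary value without completing the study.
- *Everyone who leaves before Day 36 is in the FAS.* A subject lost before any post-baseline assessment is not.
- *The loss is silent.* That fits the FAS reading only.

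The wording in 8.1 and 8.5.4, running from baseline to Visit 7, could also be read as covering the interval. No interval summary is defined, so this reading supplies no rule.

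**Conclusion.** The gap is real and worth closing before analysis. As written, the primary Visit 7 result rests on observed subjects only, under either candidate for the primary set, and the conflict between 8.4.2 and 8.5.4 leaves open whether that happens by default or by design.

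The size is conditional. A reader might infer from the third row of the table that the plan overstates success by 20 points (60% against 40%). The documents do not support that as a finding: they define no success grade, the counts are assumed, the five allowed losses are from study completion rather than from Visit 7, and the same row allows an error of 13 points the other way (73.3% against 60%). Section 8.5.4 also introduces exact intervals for secondary endpoints, so there is no planned primary percentage to correct. What does not depend on the assumed counts is the distance between the bounds: m/15, which is 33 points if five are missing and less with fewer losses. A favourable bias is plausible from the listed reasons for leaving, but the documents quantify neither its direction nor its size.

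**What to change.** In 8.5.4, with 8.4.2, 8.4.3 and 7.6.1 brought into line:

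1. Name one primary efficacy set.
2. Keep RTOG grade at Visit 7 as the endpoint and state in advance the grade cut-off that counts as success.
3. Report the proportion over all treated subjects, using the ITT set already defined in 8.4.1, with subjects lacking a Visit 7 grade in their own row, broken down by reason.
4. Count subjects who left before Visit 7 because of an adverse event, mucositis, intolerance or death as not a success. Set the remaining missing grades all to failure and then all to success, and give both proportions with exact 95% intervals. The bounds in the working are the widest case, because they leave all five losses open.
5. Do not substitute the worst earlier grade for subjects who have a Visit 7 grade; that would replace the stated endpoint.
6. For NRPS, give the number missing at Visit 7 and the last available score by reason in a separate row, not merged into the Visit 7 mean. Section 1.1 ties severity to radiation dose, so an early last score can flatter a leaver.

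The cost is a few sentences and one extra table, with no new data collection. The headline figure may come out less favourable.
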